### **METHODS**

**Setting:** The study will be conducted in two cities, New York and Indianapolis, in the EDs of their respective academic institutions—NYU Langone Medical Center and Indiana University Health University Hospital. The NYU Ronald O. Perleman Center for Emergency Services sees >60,000 patients annually. In 2015 the numbers of ED patients >75 years who were discharged to home were >3700 in the NYU ED and 2400 patients in the Indiana University Eskanazi and Methodist EDs.

**Aim1: Recruit and randomize a sample of 900 patient-caregivers (CGs) dyads (1800people total) presenting to the ED and test whether the POISED intervention will reduce recurrent acute care use over 6 months when compared with post-ED care for patients and CGs without POISED.**

**Study Design:** We will randomize subjects to either usual care or interventional groups where we will perform an initial assessment and provide a novel care management intervention for family CGs of ED users with cognitive impairment and likely ADRD.

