***Inclusion/Exclusion Criteria for Care Recipients:***

Inclusion criteria for participation in care management or usual care are as follows:

- 1) Must be 75 years and older
- 2) Must be in the emergency department for care at the point of recruitment
- 3) Must be English- or Spanish-speaking
- 4) Must have a family member or friend who provides caregiving assistance
- 5) Must have a plan to be discharged to home
- 6) Must have scored < 4 on the MiniCogTM15-19 or if using caregiver assessment by IQCODE, must be > 3.4
- 7) Must have capacity to consent or have a proxy.

Exclusion criteria for participation in care management or usual care are as follows:

- 1) Care recipient (CR) is a resident of a nursing home or other supportive facility
- 2) CR scores  $\geq 3$  on the MiniCogTM or the caregiver assessment by IQCODE was  $< 3.4$
- 3) Caregiver (CG) declines participation
- 4) CR is not being discharged to home

CR does not allow their family member or emergency contact to be contacted

Note: If the care recipient lacks capacity and we cannot obtain consent from their proxy, we will not access those data or include them in any analyses. Please note that a caregiver can still participate in the study with the assent of the care recipient, without the use of the health care data.

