*Usual Care Group:* The comparison group, those randomized to usual care (UC), will receive referrals to services at the time of enrollment. The usual care group will not receive the POISED structured assessment, attention to chronic disease management, or RCA related to the ED visit. Similar to intervention group, we will provide UC patients with a laminated card showing the Stress Thermometer™ (Appendix 5) for use in follow-up interview assessments.

**Specific Aim 1 Measures – Emergency Department (ED) Use:** We will obtain consent from patients to enable review of their medical records. We will identify all ED visits for the year prior to the index ED visit/study enrollment and for one year after enrollment. We will also search all-payer databases (APD) New York and the Indiana State Network for Patient Care to identify any episode of ambulatory or acute care that occurred within the 6 months of enrollment (6-month intervention and 6-month follow-up) and the 12 months prior to enrollment. Using the Care Recipient medical records, we will determine any prior diagnoses of dementia. We will also use the Care Recipient's medical records to determine comorbidity and root cause for ED use.

A one-item survey question will identify any additional visits that might have occurred outside the indicated state regions. For descriptive purposes, ICD discharge diagnoses will be included for any ED use. We will structure continuous variables that describe the number of ambulatory and/or acute care episodes.

**Aim 2: Develop a collaborative care plan with the interventional group and schedule follow up testing to assess whether the 6-month POISED intervention will improve family caregiver “activation” in managing the health care of care recipients compared with post-ED care without POISED at 3 and 6 months.**

*Strategy:* The POISED care management team consisting of specially-trained nurses functioning as care managers (CMs) and para-professionals in the role of care manager assistants (CMAs) will work to create an individualized care plan through the lens of cognitive impairment with an emphasis on coordinating care with the patient's primary care provider (PCP) and achieving relevance with the goals and capacity of the family CG and CR.

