*The second stage of recruitment and consent is consent of the Care Recipient for access to health records.* After it is determined that the Care Recipient has an eligible Caregiver, the Care Recipient will be approached regarding allowing the research team access to their medical records. Capacity is determined for the CR for consent using a common sense procedure. This is possible because the request in question is easy to understand procedure (collecting information from the health record). We anticipate that most will demonstrate capacity to decide regarding use of their medical records. For those who do not, we will use a proxy consent –the caregiver if that person is next of kin (defined based on hierarchy: spouse, child, sibling, nephew or niece) in the absence of a DPOA for healthcare or by consenting the proxy who is DPOA but not present, which again will require discussion of the consent process via telephone using an IRB approved script and mailing the original consent for to be signed or returned via mail, fax, or SendSafe email procedure for e-consent. If the care recipient does not want us to use his/her medical records we will of course not do so and for those subjects, and this will be missing data. This is a minimal risk study with a chart review being completed 6 months later; we will not require capacity to be reassessed at the end of the 6 months. We request consent at the beginning of the study because this is an element of the research protocol and both caregivers and care recipients need to be aware and agree with participating given this approach. Loss of capacity after giving permission does not negate this consent and require a new consent procedure but a caregiver (legal healthcare proxy) under these circumstances, can override the consent at any point in the study if in the future, the proxy does not want us to have access to the chart at the end of 6 months. The Care Recipient, as the consenting individual, can also always rescind their earlier consent. Please note that at the time of capacity assessment, the only clinical information that we have on this patient is that they have performed below a pre-specified cut point on a simple 2 minute cognitive screening test. This result neither indicates a definitive diagnosis of dementia, nor any level of severity of cognitive impairment.

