*The third stage of consent is for participation in care management or usual care and randomization into one of two treatment arms – receipt of the Program of Intensive Support in Emergency Departments for Care Partners of Cognitively Impaired Patients (POISED-CPCIP) or usual care. The Caregiver can be included regardless of CR health record consent.*

Randomization will occur after completion of the baseline interview. Here, the caregiver will consent for himself or herself. Capacity will be determined for the Caregiver. For the care recipient, we will use an assent procedure, in which the Care Recipient has authority to decline participation on behalf of the Caregiver.

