### **Vulnerable Populations**

Care Recipient: The study will involve caregivers of patients with cognitive impairment and the healthcare data of those with cognitive impairment. The risk for care recipients are minimal due to the nature of their part of the study, which is limited to a chart review. To protect individuals with cognitive impairment, the research assistant will require consent from the caregiver and will assent the care recipient for the participation of their Caregiver in a care management program, and care recipient consent for health record access. If the care recipient refuses participation through any form of rejection, then that dyad will not be considered for the study. Care recipients subjects in this study insofar as they have given the research team permission to access their health records. Because we are working with family caregivers, care recipients may or may not be indirectly involved with the clinical support given to caregivers. Although we have never been required to involve the care recipients in consent procedures for the purpose of involving the caregivers as participants in other similar funded trials, we are offering (out of respect to these individuals) the opportunity to have them decline our involvement with their caregiver even if the caregiver wants to participate. However, because we are collecting information from their chart, a consent procedure will be necessary for this small component. The Care Recipient will have the right to decline participation on the part of their family caregiver even if they do not have capacity to do so. Moreover, they can decline participation at any time during the study duration and we will no longer include that caregiver in our research procedures or use their data. This approach is in keeping with our commitment to ensuring the highest level of respect for these individuals.

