### **Process of Consent**

Potential subjects will be identified from the ED on the basis of the cognitive state of the ED patient. Family caregivers will be identified and approached in the ED and if not present, will be contacted by phone and offered participation in the study. Caregivers and/or care recipients who are in the ED will only be approached only after giving permission to ED staff who will alert the research assistant of a potential caregiver-care recipient. Should phone recruitment be in effect, the family caregiver will be identified through the EMR or via patient and will complete the IQCODE to determine eligibility. Should the family caregiver screen into the study via IQCODE, they will be offered participation in the study.

Trained Research Associates (RAs) will approach caregivers presenting to the Emergency Department with eligibility criteria. The RAs will also provide the caregiver and care recipient with the consent form that contains all pertinent study and contact information, and will describe the nature of the study to the dyad. The care recipient will be asked to explain their understanding that we will be accessing their medical records to obtain data through the Evaluation to sign consent (ESC) form, and then verbally consented to participate. Because this is a simple procedure to understand, we anticipate that most will demonstrate capacity. For those who do not, we will use a proxy consent – typically the caregiver if that person is next of kin (defined based on hierarchy: spouse, child, sibling, nephew or niece) in the absence of a DPOA for healthcare or by consenting the proxy who is DPOA but not present, which will require telephone and waiver of written consent. This will require telephone verbal consent with waiver of written documentation of consent, as well as written authorization submitted via mail

or fax. If the care recipient does not want us to use his/her medical records we will of course not do so and for those subjects, and this will be missing data.

The caregiver will be asked to summarize the study, using the Evaluation Signed Consent (ESC) form, and consent to participate. The RAs will determine if the caregiver understands the study and that participation is voluntary and will not affect the care the Care Recipient receives in the Emergency Department.

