Sample Size and Power Consideration: Sample size for the proposed study is estimated for achieving 80% power in reducing acute care use in the POISED group compared with the usual care group in Specific Aim 1. A previous study had reported a 30-day readmission rate of 58% in dementia patients as compared to 38% in those without dementia. Given that our patient sample may include less severe cognitive impairment with less ED use, we assume, conservatively, that the rate of ED visits in the usual care group is 40%. With 320 patients enrolled per group, we will have 82% power to detect an odds ratio of 0.62 for repeat ED visits in the POISED group compared to the usual care group at the 0.05 significance level. This detectable odds ratio is equivalent to reducing the ED visit rate to 29% or lower in the POISED group compared with the 40% assumed for the control group. The use of stratified randomization ensures that patients in the intervention and control groups are similar on the stratification variables, thus reducing the variance of the difference between the two group means and resulting in greater power than simple randomization. Therefore, actual power for our study will be higher than projected here. Since we will be using EMR for acute care data and phone follow-up to supplement out of network use, we anticipate complete data from all study participants for this aim.

For Aims 2 and 3, assuming that 205 (64%) dyads will complete the 6-month evaluation (see Figure 2), we will have 80% power to detect an effect size of 0.28 or greater on the CG activation score, PHS-9, GAD-7 and MOS scores between POISED group and the control group using a two-sample t-test at the 0.05 significance level. The detectable effect size of 0.28 used in our power estimation is reasonable and justified given that previous studies on collaborative care management of dementia patients have shown an effect size of 0.45 SD on a number of caregiver psychosocial outcomes. Our previous studies have found a mean PHQ-9 score of 4.4 (SD=5.6), and a mean GAD-7 score of 3.2 (SD=3.5). Thus our projected effect size will allow us to detect a change as small as 1.6 on the PHQ-9 and 1 on the GAD-7. As described above, the use of stratified randomization will provide greater power than those projected here.

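### The Aim 1 power assumes no missing outcomes, yet dyads may be enrolled without access to the care recipient's records

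*Combined protocol and SAP*

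**What the plan says.** **Power.** The Statistical Plan (Sample Size and Power Consideration) sizes the trial on Aim 1: 40% of usual-care patients with a repeat ED visit, an odds ratio of 0.62 (29% or lower under POISED), 320 patients enrolled per group, 82% power against an 80% target, at the 0.05 level. Because ED use will come from the electronic record, with telephone follow-up for out-of-network visits, "we anticipate complete data from all study participants for this aim".

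**Record access.** The note under the Inclusion/Exclusion Criteria for Care Recipients says that "a caregiver can still participate in the study with the assent of the care recipient, without the use of the health care data". It adds that where the care recipient lacks capacity and no proxy consents, the data are neither accessed nor analysed. Recruitment, Consent and Assent, in the stage that covers randomisation, says: "The Caregiver can be included regardless of CR health record consent". For care recipients who decline use of their records it says: "we will of course not do so and for those subjects, and this will be missing data". Process of Consent repeats this. Consent can also be rescinded or overridden by a proxy later (Recruitment, Consent and Assent), and the care recipient can decline at any time, after which the data are not used (Vulnerable Populations).

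**Role of the interview.** Specific Aim 1 Measures starts from medical records and state databases and gives the caregiver's answer a supplementary role: "A one-item survey question will identify any additional visits that might have occurred outside the indicated state regions".

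**Number of dyads.** Aim 1 in the Methods reads: "Recruit and randomize a sample of 900 patient-caregivers (CGs) dyads".

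**The concern.** The sample-size section expects nothing to be missing for the outcome that sets the sample size. The consent sections describe a route by which the main source of that outcome is unavailable, and they call the result missing. These statements cannot all stand as written.

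Two things are at stake. The first is the stated power, which has little slack at 320 per group. The second is that the reader cannot tell what 320 counts: all randomised dyads, or only care recipients whose records can be read. In the order written, a refusal of record access comes before randomisation and so mainly costs precision. A later withdrawal comes after it and could differ between arms.

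**Working it through.** **Inputs** (Sample Size and Power Consideration): control rate p1 = 0.40; odds ratio 0.62, or p2 = 0.29 as stated; n = 320 per group; alpha 0.05. Sidedness is not stated, so two-sided is assumed.

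**Rate implied by the odds ratio.** Odds = (0.40/0.60) × 0.62 = 0.4133, so p2 = 0.4133/1.4133 = 0.2925.

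**Reproducing the 82%.** Pooled two-proportion test without continuity correction, with p̄ the mean of p1 and p2:

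Power = Φ{ [ |p1 − p2| − 1.96 √(2p̄(1 − p̄)/n) ] / √([p1(1 − p1) + p2(1 − p2)]/n) }

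At odds ratio 0.62: difference 0.1075; 1.96 × 0.0376 = 0.0737; denominator 0.0374; Φ(0.905) = 81.7%. At p2 = 0.29 the same formula gives 83.5%. The plan's 82% is reproduced with no missing outcomes.

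**Slack at 320 per group.** 80% power needs 307 per group (odds ratio 0.62) or 292 (29%). The tolerable loss is 1 − 307/320 = 4.1%, or 1 − 292/320 = 8.8%.

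**Illustrative losses.** No document gives a rate of missing record access, so these percentages are assumptions. Each entry is power at odds ratio 0.62 / at 29%.

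| Outcomes missing | From 320 per group | From 450 per group |
|---|---|---|
| 0% | n = 320: 81.7% / 83.5% | n = 450: 92.5% / 93.6% |
| 5% | n = 304: 79.7% / 81.6% | n = 427.5: 91.2% / 92.4% |
| 10% | n = 288: 77.6% / 79.5% | n = 405: 89.7% / 91.0% |
| 20% | n = 256: 72.6% / 74.6% | n = 360: 86.0% / 87.5% |

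**The 900 dyads.** Split 1:1 this is 450 per arm. Power stays at or above 80% up to 1 − 307/450 = 31.8% missing (odds ratio 0.62) or 1 − 292/450 = 35.1% (29%). A loss of 1 − 320/450 = 28.9% would still leave 320 per arm. The gap is 900 − 640 = 260 dyads, which the visible text does not explain.

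**What 320 counts.** For Aims 2 and 3 the same section expects 205 dyads, 64%, to complete 6 months. 205/320 = 64.1%, whereas 205/450 = 45.6%. So 320 serves there as the base before interview attrition, which leans towards 320 meaning everyone enrolled. It does not settle the matter, and the figure cited at that point is not shown.

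**The case against.** **The contradiction may be only apparent.** Vulnerable Populations treats care recipients as subjects "insofar as they have given the research team permission to access their health records". If the 320 patients are only those who gave access, the 82% needs no change at enrolment. That reading is open, but the sample-size section does not state it, and it would not cover access withdrawn later.

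**The loss may be small.** Most care recipients are expected to have capacity and proxy consent is available, so a few percent is plausible. With 900 dyads the power question largely disappears. Both points stand. A reader might infer that the trial is underpowered; the documents do not support that, because they give no rate and name a target that could absorb a large loss. The plan also says that stratified randomisation will raise power, but it puts no number on the gain.

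**Caregiver report may fill the gap.** The survey in Appendix 3 asks for the number of ED visits, and Appendix 1 lists both record and survey as sources of acute use, so lack of records need not mean no outcome. But the Aim 1 measures and the sample-size section give the interview only a supplementary role, and nothing says that it replaces absent records.

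**Two stronger readings fail.** Data Collection and Documentation says that primary outcome measures come from telephone interviews. A reader might infer that interviews are the sole source of ED visits and that Aim 1 power should be computed on interview completers. That sentence does not name ED use and can be read as the caregiver scales; the stream listed just before it takes health services use from the records. A reader might also infer that the plan makes no provision for missing outcomes. It does: the paragraph on sensitivity analysis for missing data states a missing-at-random assumption and plans imputation or likelihood methods. Only its baseline comparison is restricted, to death or withdrawal.

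**Conclusion.** The complete-data expectation conflicts with the eligibility and consent text and should be replaced. The power calculation itself is sound; what fails is the zero loss behind it. At 320 per group the 80% target is lost at about 4% missing (odds ratio 0.62) to 9% missing (29%). At 450 per group it holds to about 32% even on the less favourable rate. Which case applies cannot be read from the visible text.

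This rests on a two-sided test, equal allocation and loss rates assumed for illustration. It is a should-fix point: it touches the figure on which the trial is sized, but does not invalidate the design.

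**What to change.** 1. **Sample size.** Replace the complete-data sentence with an assumed share of dyads lacking record access. Say whether 320 per group counts randomised dyads or dyads with outcome data, reconcile it with 900, and restate Aim 1 power on dyads with outcome data. This asks for no added enrolment.
2. **Outcome source.** Keep records as the main source of ED visits, and make clear that the sentence on primary outcome measures in Data Collection and Documentation does not override this. Add a sensitivity analysis that, where consent permits, uses the caregiver-reported ED visits already collected for dyads without records. State its limits: caregivers know their assignment, and a reported visit at 3 months settles the binary outcome while a report of no visit followed by dropout leaves it missing.
3. **Missingness comparison.** Add refused and withdrawn record access, by arm, to the comparison that now names death or withdrawal.

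**Cost.** Wording in the sample-size, data-source and missing-data text, plus one sensitivity analysis; no new data collection. If 320 per group proves to be the full randomised number, the stated power will be somewhat lower. Caregiver report is less accurate than records, which is one reason to keep it out of the main analysis.

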## Appendix 1: Data Variables

Table 1: Measures			
Measure	Data Source	Measure Construction	Measures refer to: CG* and / or CR*; Assessment times: 0/BL † , 3, 6, 12 month
Predisposing Fixed Characteristics			
Basic			
Age	EMR/ Survey	Years	CG, CR; 0 mo. (BL)
Gender	EMR/ Survey	Categorical: Male/Female	CG, CR; 0 mo. (BL)
Race/Ethnicity	EMR/ Survey	Categorical: White, Black, Hispanic, other	CG, CR; 0 mo. (BL)
Education	Survey	Categorical: < H.S., H.S., Some College, College graduate+	CG; 0 mo. (BL)
Prior (1-year) non-acute use	EMR/ Survey	Counts: physician ambulatory visits, in-home supportive services	CR; 0 mo. (BL)
Prior (1-year) acute use	EMR/ Survey	Counts: physician ambulatory visits, ED, hospital visits / bed days	CR; 0 mo. (BL)
ADRD-Specific			
Dementia Type	EMR	Categorical: including AD, Lewy Body disease, Parkinson's Disease, Vascular, Frontotemporal, and mixed	CR; 0, 3, 6 mo.
Caregiver relationship to CR	Survey	Categorical: Spouse, child, other relative, friend/other	CG, CR; 0 mo.
Functional State	Survey	14 items: ADL/IADL for CG; within HABC-M ‡ for CR	CG, CR; 0, 3, 6 mo.
Marital Status	Survey	Categorical: Single/never married, married, divorced, widowed	CG, CR; 0, 3, 6 mo.
Substance use history	Survey	Current: Yes/No; Past history: Yes/No	CG, CR; 0, 3, 6 mo.
Mental illness history	Survey	Yes/No: Depression, schizophrenia, PTSD, other	CG, CR; 0 mo.
Enabling Time Varying Effect Characteristics			
Basic			
Distance to hospital (ED)	Calculated	Miles	CG, CR; 0, 3, 6 mo.
Distance to usual source of care (USC)	Calculated	Miles	CG, CR; 0, 3, 6 mo.
Difference in distance ED vs. USC	Calculated	Miles (USC) – distance to hospital	CG, CR; 0, 3, 6 mo.
Change in PCP	Survey	Yes/No	CR; 0, 3, 6 mo.
Insurance	EMR	Yes/No	CR; 0, 3, 6 mo.
Current non-acute use	EMR/ Survey	Counts: physician ambulatory visits, in-home supportive services	CR; 0, 3, 6, 12 mo.
Current acute use	EMR/ Survey	Counts: physician ambulatory visits, ED, hospital visits / bed days	CR; 0, 3, 6, 12 mo.
ADRD-Specific			
Mode of transportation	Survey	Categorical: personal car, taxi, train, bus, walk	CR; 0, 3, 6 mo.
Caregiver living arrangement	Survey	Categorical: Live with subject, close proximity (miles), other	CG; 0, 3, 6 mo.
Caregiver stress	Survey	Stress thermometer (scale), 5-level visual analogue scale *	CG; 0, 3, 6, 12 mo.
Dementia symptoms	Survey	HABC-M ‡ (measuring severity of CR symptoms)	CR; 0, 3, 6 mo.
Need Characteristics			
Basic			
Acute illness	Survey	Counts: episodes by type (classification by study physicians)	CR; 0, 3, 6 mo.
Falls, other injuries	Survey	Counts: episodes by type (classification by study physicians)	CR; 0, 3, 6 mo.
Non-acute illness	Survey	Counts: episodes by type (classification by study physicians)	CR; 0, 3, 6 mo.
Medication need for refill	Survey	Categorical: Yes/No	CR; 0, 3, 6 mo.
Clinical co-morbid conditions	EMR	Charlson comorbidity index *	CR; 0, 3, 6 mo.
Satisfaction	Survey	Scale: 0-10 (worst possible care to best possible care * )	CG; 0, 3, 6 mo.
ADRD-Specific			
Functional State	Survey	14 items: ADL/IADL for CG; within HABC-M ‡ for CR	CG, CR; 0, 3, 6 mo.
Behaviors	Survey	BEHAVE 5+ *	CR; 0, 3, 6, 12 mo.
Caregiver Activation	Survey	MYLOH™ Instrument *	CR; 0, 3, 6, 12 mo.
Social Support	Survey	MOS Abbreviated Social Support (4-item; 5-point Likert scale) 	CG; 0, 3, 6 mo.
Other root causes	EMR	Application of post-hoc adjudication of root causes for ED use	CR; 0, 3, 6 mo.

\*LEGEND: Caregiver= CG; Care Recipient = CR; Baseline = BL

